6.3.6 Laboratory Evaluations

At screening and entry all protocol required laboratory values must be recorded on CRFs. For post-entry assessments, record on CRFs all Grade ≥ 2 laboratory values. All laboratory toxicities that led to a change in treatment, regardless of grade, must be recorded on CRFs. Record on CRFs all values for serum creatinine, AST, ALT, and fasting lipid panel regardless of grade.

Hematology

Hemoglobin, hematocrit, white blood cell count (WBC), differential WBC, and platelet count.

Liver Function Tests/Chemistries

Total bilirubin (and indirect bilirubin if subject is receiving atazanavir), ALT (SGPT), AST (SGOT), and alkaline phosphatase, blood urea nitrogen (BUN), creatinine, glucose, sodium, potassium, chloride, and CO₂/bicarbonate.

Fasting Lipid Panel

Total cholesterol, HDL-c, calculated LDL-c (if triglycerides <400 mg/dL) and triglycerides.

Hepatitis Testing (at Screening)

Hepatitis B surface antigen, Hepatitis C antibody (if indicated, Hepatitis C RNA PCR).

Prothrombin time/INR/PTT

Prothrombin time/INR and PTT are required at pre-entry for rectal tissue subset only.

Rectal GC/CT NAAT

Rectal swab for GC/CT NAAT will be obtained for rectal tissue subset only

HSV Antibody

Serum for HSV antibody testing will be obtained at Entry visit for the rectal tissue subset only

Pregnancy Test

For women of reproductive potential as defined in section 4.1.11, serum or urine β -HCG (urine test must have a sensitivity of at least 50 mIU/mL) must be performed as indicated in section 6.1:

- At the screening visit.
- At the study entry visit.
- Every 4 weeks during study participation.

6.3.7 Immunologic Studies

CD4+

Obtain absolute CD4+ T-cell count and percentage within 60 days prior to entry from a laboratory that possesses a CLIA certification or equivalent.

Evaluations for CD4+/CD8+ T-cell counts and percentages will be performed in the same laboratory at the entry visit and throughout the course of the study.

Because of the diurnal variation in CD4+ and CD8+ T-cell counts, determinations for individual subjects should be obtained consistently in either the morning or the afternoon throughout the study, if possible.

6.3.8 Virologic Studies

Plasma HIV-1 RNA

All measurement of HIV-1 RNA will be performed by a laboratory that possesses a CLIA certification or equivalent. Screening HIV-1 RNA must be performed within 60 days prior to study entry. Eligibility will be determined based on the screening value.

6.3.9 Stored Samples

Blood and rectal tissue will be processed immediately after collection and stored for future analysis. Results of these tests do not have clinical relevance and will not be reported to participants.

Stored Specimens for Cellular Immune Activation

PBMC will be stored for batched analysis:

Immunology Lab:

- Markers of cellular immune activation
- Cell cycling (Ki67)
- Immunoregulatory cell subsets (frequency and phenotype)
- CD39 and CD73 expression in lymphocytes and monocytes

Stored Specimens for Markers of Inflammation, Coagulation and Activation

Plasma specimens for batch measurement (Immunology Lab):

- Soluble markers of immune activation, inflammation, and coagulation

Stored Specimens for Adenosine and DP Pharmacokinetics

Plasma and Urine Specimens for HPLC-tandem mass spectrometry ([name] Lab) of:

- Adenosine, inosine, guanosine
- 5'-AMP and 3,5'-cAMP
- Plasma creatinine
- Dipyridamole assay

Stored Specimens for Virology:

PBMC and Plasma ([name] Lab):

- Cell-associated HIV-1 DNA
- Cell-associated HIV-1 RNA
- HIV-1 RNA Single copy assay

Rectal Mucosa:

Tissue mononuclear cells for immune activation (Mucosal Immunology Lab):

- Markers of cellular immune activation
- Immunoregulatory cell subsets
- Expression of CD39 and CD73 in lymphocytes and monocytes

Tissue mononuclear cells for virology ([name] Lab):

Cell-associated HIV-1 DNA
Cell-associated HIV-1 RNA

Refer to the protocol laboratory processing chart (LPC) for details of collection, processing, and storage.

6.3.10 Brachial Artery FMD

The brachial FMD assessment will be performed and interpreted at the University of Pittsburgh Department of Epidemiology Ultrasound Research Lab (URL) as per Section 6.1.

Subjects who are prematurely discontinuing the study should have a brachial FMD test only if it has been ≥ 4 weeks since the last FMD assessment.

Considerations for the Brachial Artery FMD Scanning:

1. Subjects should fast and abstain from exercise and smoking for at least 8 hours prior to the study visit and be afebrile (afebrile (oral T < 38 degrees C), at the visit; otherwise these assessments must be rescheduled.
 - a) Subjects should be fasting (nothing but water or black decaffeinated coffee for 8 hours prior to evaluation; drinking black decaffeinated coffee is considered an exception but is not advised).
2. No blood pressure (BP) measurements or venipuncture are permitted in the right arm before the ultrasound scan.
3. FMD assessments should be done in the morning, approximately at the same time.

Brachial artery size in response to an endothelium-dependent stimulus will be evaluated by ultrasonographic measurement of the brachial artery. Baseline brachial artery diameter will be measured using 2-D ultrasonography. A blood pressure cuff will be placed proximal to the brachial artery and will be inflated to suprasystolic pressure (cuff inflation will be 40mmHg above the systolic blood pressure) for 5 minutes. After 5 minutes, the cuff will be deflated. Brachial artery diameter will be measured by 2-D ultrasonography at 1 minute following cuff deflation to measure brachial artery diameter response to reactive hyperemia, which is an endothelium-dependent vasomotor stimulus.

For quality control purposes, a subset of participants may be asked to have a second FMD at Weeks 4, 12, or 24.

6.3.11 Rectal Exam and Rectal Specimen Collection

Rectal tissues will be obtained from subjects at Enrollment and at Weeks 12, 24, and 28. These study visits will take place at the Magee Womens Hospital CTRC. Procedures will be performed by qualified physicians who perform rectal biopsies on a regular basis. All subjects in the Tissue Subset will be instructed to abstain from receptive anal intercourse and all rectal products for 72 hours prior to rectal biopsy, and for 7 days post-biopsy to minimize risk of bleeding complications. Subjects will be contacted by telephone 24-48 hours after sample collection to assess for any AEs.

The subject will be positioned in the left lateral decubitus position for the following procedures:

- Rectal swab for GC/CT
- Visual and digital rectal exam: The examiner will conduct a visual examination of the anus and surrounding area and note any abnormality. The examiner will then insert a lubricated gloved finger into the anal canal and sweep around the internal anal circumference.
- Enema: A 125 mL saline enema will be inserted through the anus and the contents gently squeezed into the rectum. The subject will hold the fluid in the rectum for 5 minutes then expel it.
- Flexible sigmoidoscopy and biopsy: A flexible sigmoidoscope will be inserted to approximately 10-20 cm, where approximately 17-21 biopsies will be taken using large-cup biopsy forceps.

6.3.12 Medication Adherence Assessment

A standardized assessment to monitor adherence and pill counts will be administered. Subjects will be instructed to return pill bottles for DP to the study site, and pill counts will be undertaken by the study nurse or designee and recorded on the CRFs.

6.3.13 Pre- and post-bronchodilator spirometry (for participants enrolled under Version 2.0)

Participants will be asked to withhold use of any short-acting bronchodilators for at least 4 hours prior to testing and long acting bronchodilators for at least 12 hours prior to testing. At least 3 acceptable forced vital capacity maneuvers should be performed according to ATS standards: a maximal inspiration followed by a maximal forced expiratory effort which lasts for at least seconds. The participant should be seated. Ensure that the 3 best FEV1 values are within 5% of each other. Participants will then be given 4puffs (360ug) of albuterol from a metered dose inhaler through a spacer. Three acceptable forced vital capacity maneuvers will again be performed according to ATS standards. Refer to the Manual of Procedures (MOPS) for detailed instructions.

7.0 CLINICAL MANAGEMENT ISSUES

Criteria for subject management, dose interruptions, modifications, and discontinuation of treatment will be mandated only for toxicities attributable to DP.

The grading system is located in the DAIDS Table for Grading the Severity of Adult and Pediatric Adverse Events Version 1.0 - December 2004 (Clarification dated August 2009), which can be found on the Division of AIDS Regulatory Support Center Web site: <http://rsc.tech-res.com/safetyandpharmacovigilance/>.

The management of toxicities suspected to be due to ART should be according to standard clinical practice.

7.1 Toxicity

7.1.1 General Reactions

- Grade 1 or 2

Subjects who develop a Grade 1 or 2 AE or toxicity, except as stated in Section 7.2 may continue study treatment at the discretion of the investigator. If a subject chooses to discontinue study treatment, the subject will be followed until the toxicity resolves.

- Grade 3

Subjects who develop a Grade 3 AE that is not specifically addressed below and is judged by the investigator to be study drug-related should have the study drug held. Subjects should be followed closely and if the AE does not return to Grade ≤ 2 within 4 weeks, the study drug must be permanently discontinued with subject evaluations as per Section 6.2.4.

If the study drug is resumed and the same Grade 3 AE recurs within 4 weeks of reintroduction, and the investigator considers this AE related to the study drug, the drug must be permanently discontinued.

With a Grade 3 AE that is judged not related to the study drug by the investigator, the study drugs may be continued at the discretion of the site investigator with close follow up.

Subjects experiencing Grade 3 AEs requiring permanent discontinuation of study treatment should be followed closely for resolution of the AE to Grade ≤ 2 .

Subjects with Grade 3 asymptomatic laboratory abnormalities in cholesterol, creatine kinase (CK) or triglycerides may continue study treatment.

- Grade 4

Subjects who develop a Grade 4 AE that is not specifically addressed below and is judged by the site investigator to be study drug-related should have the specific study drug held. Clinical assessments and laboratory testing will be completed as described for Grade 3 toxicity. Subjects experiencing Grade 4 AEs should be followed closely with additional clinical assessments and laboratory testing as clinically indicated until resolution of the AE.

7.1.2 AST/ALT Elevations

- Grade 2 Asymptomatic

For subjects who develop asymptomatic Grade 2 AST or ALT elevations, DP may continue and the AST and ALT should be repeated within 2 weeks.

- Grade 2 Symptomatic

For symptomatic Grade 2 or greater elevations of AST or ALT for subjects on DP, the study drug should be held until symptoms have resolved and further evaluations, as indicated, have been conducted. If symptoms resolve and AST or ALT returns to < Grade 2, then DP may be resumed with close follow up.

- Grade 3

Subjects who develop a Grade 3 AST or ALT that is judged by the investigator to be related to DP should have the DP held. The subject should be followed closely and if the AE does not return to Grade ≤ 2 within 4 weeks, the DP must be permanently discontinued with subject evaluations as per Section 6.2.4.

If the study drug is resumed and the same Grade 3 AE recurs within 4 weeks of reintroduction, and the investigator again considers this AE related to the DP, the drug must be permanently discontinued.

- Grade 4

Subjects who develop a Grade 4 AST or ALT AE that is judged to be related to DP by the investigator will have the drug permanently discontinued, with clinical assessments and laboratory testing as described for Grade 3 toxicity. Subjects experiencing Grade 4 AEs should be followed closely with additional clinical assessments and laboratory testing as clinically indicated.

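### Under Section 7.1.2, a symptomatic DP-related Grade 4 AST/ALT elevation, and some symptomatic DP-related Grade 3 ones, may be resumed under one rule and must be permanently stopped under another

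*Combined protocol and SAP*

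**What the plan says.** Section 7.1.2 sets out AST/ALT management in separate paragraphs. Three of them matter here.

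- **Symptomatic paragraph.** Its heading is "Grade 2 Symptomatic", but its sentence is wider: "For symptomatic Grade 2 or greater elevations of AST or ALT for subjects on DP, the study drug should be held" until the symptoms are gone. It continues: "If symptoms resolve and AST or ALT returns to < Grade 2, then DP may be resumed with close follow up". It sets no upper grade, no time limit and no condition that the event be related to DP.
- **Grade 3 paragraph.** "Subjects who develop a Grade 3 AST or ALT that is judged by the investigator to be related to DP should have the DP held", and "if the AE does not return to Grade ≤ 2 within 4 weeks, the DP must be permanently discontinued". A second trigger follows: "If the study drug is resumed and the same Grade 3 AE recurs within 4 weeks of reintroduction" and the investigator again judges it related, DP is stopped for good.
- **Grade 4 paragraph.** A subject with a Grade 4 AST or ALT event "judged to be related to DP by the investigator will have the drug permanently discontinued". It offers no route to resumption.

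Neither the Grade 3 nor the Grade 4 paragraph is restricted to asymptomatic events. Section 7.0 adds that management criteria are mandatory only for toxicity attributable to DP. Section 8.1 lists drug-related toxicity as a reason for permanent discontinuation, but only by pointing back to Section 7.1.

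**The concern.** A toxicity rule should give one answer for one clinical picture. Here two paragraphs of the same section can apply to the same subject at the same time and give different answers on whether DP may be restarted.

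Three things are at stake.

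- **Safety.** The precautions in Section 2.3 report hepatic enzyme elevations and hepatic failure with DP, so these paragraphs deal with a recognised risk of the drug.
- **Retention.** Under Section 6.2.4, a subject who stops treatment prematurely has a discontinuation visit and then leaves the study. The paragraph an investigator follows can therefore decide whether follow-up continues.
- **Endpoint.** Treatment discontinuation is a secondary endpoint in Section 9.2.2. A stopping rule with two readings makes that count depend partly on who reads it.

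**Working it through.** No arithmetic applies, because the point rests on no sample size, power or event count. The check applies each paragraph of 7.1.2 to each type of event and compares the results.

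| Case (AST/ALT) | Symptomatic paragraph | Grade 3 or Grade 4 paragraph | Result |
|---|---|---|---|
| (a) Grade 4, symptomatic, DP-related; later symptom-free and below Grade 2 | May resume | Permanent stop | Conflict |
| (b) Grade 3, symptomatic, DP-related; still Grade 3 at 4 weeks, later symptom-free and below Grade 2 | May resume | Permanent stop | Conflict |
| (c) Grade 3, symptomatic, DP-related; recurs within 4 weeks of restarting, again judged related, then resolves | May resume | Permanent stop | Conflict |
| (d) Grade 3, symptomatic, DP-related; at exactly Grade 2 within 4 weeks | Resumption condition not met; stays held | Permanent stop not triggered; no separate resumption threshold stated | Compatible |
| (e) Grade 3, symptomatic, DP-related; symptom-free and below Grade 2 within 4 weeks, no recurrence | May resume | Permanent stop not triggered | No conflict |
| (f) Grade 3 or 4, symptomatic, not DP-related | Hold, then may resume | Does not apply | No conflict with the Grade 3 and 4 paragraphs; attribution unclear (below) |
| (g) Grade 2, symptomatic | Hold, then may resume | Does not apply | No conflict |

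**Is there a precedence rule?** The general Grade 3 and Grade 4 rules in Section 7.1.1 expressly give way to the specific rules that follow them. Section 7.1.2 has no such clause between its own paragraphs. Section 8.1 refers back to 7.1 and so cannot settle the matter.

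**Attribution.** The Grade 3 and Grade 4 paragraphs require a judgment that the event is related to DP. Section 7.0 limits mandatory criteria in the same way, and Section 7.1.1 leaves continuation after an unrelated Grade 3 event to the investigator. The symptomatic paragraph states a hold and is silent on attribution.

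**Effect on the week-12 primary analysis set.** Section 9.5 keeps subjects who stay on treatment through week 12 with no more than 7 consecutive days missed.

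- In case (b) the two paragraphs part only after a 4-week hold, which is 4 × 7 = 28 days. If those 28 days end before week 12, the subject is excluded under either rule, since 28 > 7. If they end later, the subject's status up to week 12 is the same under both.
- In case (a) the choice of paragraph matters only if the days held before week 12 number 7 or fewer.
- In case (c) the same limit must be met for both the first hold and the hold after recurrence.
- Events after week 12 cannot change the set.

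**The case against.** The strongest reply is that the paragraphs can be read together. The symptomatic paragraph is permissive (*may*), while the Grade 3 and Grade 4 paragraphs are mandatory (*must*, *will*). An investigator who holds DP for symptoms and then stops it for good after a related Grade 4 event breaks neither rule. The layout by grade and the Grade 2 heading point the same way: symptoms trigger a hold, and the later paragraphs add stricter limits.

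That reading is plausible, but the reader has to supply it. The operative sentence reaches beyond Grade 2, its heading does not, and nothing says which paragraph prevails. On the page there remains a written permission to resume after a symptomatic, related Grade 4 event.

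Several stronger readings are tempting, and here the objection is right.

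- A reader might infer that the two recovery thresholds (below Grade 2, and Grade 2 or lower) contradict each other. They answer different questions: when DP may restart, and when it must stop for good. At exactly Grade 2, DP simply stays held (case (d)).
- A reader might infer that the symptomatic hold is mandatory whatever the cause. Section 7.0 limits mandatory criteria to toxicity attributable to DP. What stands is that the paragraph does not carry that condition itself.
- A reader might infer that every symptomatic Grade 3 or 4 event is affected. Cases (e) and (f) show otherwise.
- A reader might infer that these rules decide who enters the week-12 analysis. The 7-day limit leaves that almost no room.
- A reader might rank these as the gravest foreseeable drug events. The documents do not rank them; Section 2.3 also lists severe bronchospasm and angioedema.

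**Conclusion.** The concern holds in a limited form. The resume-or-stop conflict covers symptomatic, DP-related Grade 4 AST/ALT elevations that later resolve. It also covers symptomatic, DP-related Grade 3 elevations that are not at Grade 2 or lower within 4 weeks, or that recur within 4 weeks of restarting, before they resolve. Beside it stand a heading that disagrees with its own sentence and an attribution condition missing from one paragraph of three.

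The number of affected subjects cannot be computed, because the documents give no rate for such events. I assume it is small, possibly zero, in about 40 subjects at one site. The weight of the point lies in subject safety and in a clean definition of treatment discontinuation. No material effect on the week-12 primary analysis or on power is shown. It is a drafting defect in a safety rule, and worth correcting because the correction is cheap.

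The conclusion assumes that no precedence rule exists outside the documents reviewed, for example in the Manual of Procedures.

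**What to change.** The sponsor should reconcile the heading, the symptomatic paragraph, and the Grade 3 and Grade 4 paragraphs of 7.1.2, and align the attribution condition with Section 7.0. Each combination of grade, symptoms and attribution should fall under exactly one rule for holding, resuming and permanent discontinuation. A small table indexed by those three factors would show any remaining overlap or gap. If one paragraph is meant to override another, the text should say so.

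Which rule applies to which event is the sponsor's clinical decision, and this review takes no view on it.

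The cost is a wording change in one section, by amendment or clarification memo. No subjects, visits or procedures are added.

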7.1.3 Hypotension

- Grade 2

Subjects who develop a symptomatic hypotension that resolves with oral fluids (Grade 2) may continue study medication and will be instructed to maintain adequate hydration. Recurrence of Grade 2 hypotension should prompt consideration of discontinuation of study treatment.

- Grade 3

Subjects who develop Grade 3 or 4 hypotension that is judged by the investigator to be related to DP will have study treatment permanently discontinued.

7.1.4 Headache

- Grade 1

Subjects who develop Grade 1 headache may continue study medications.

- Grade 2

Subjects who develop Grade 2 headache may continue study medication and may be treated with over the counter analgesics (acetaminophen preferred, NSAIDS should be avoided and may not be taken for > 3 consecutive days).

- Grade 3

Subjects who develop Grade 3 or 4 headache that is judged by the investigator to be related to DP will have study treatment permanently discontinued.

7.2 Pregnancy Management

If the pregnancy test is positive at entry, then the subject must not start study treatment. No further evaluations are necessary, provided that the subject did not initiate study drug.

Subjects who become pregnant after study entry must discontinue study treatment immediately. These subjects should be seen for a premature treatment discontinuation evaluation within 7 days. No further study evaluations except for safety labs will occur. These subjects will complete a study termination visit per Section 6.1. Study staff will request permission to contact pregnant participants by telephone monthly regarding pregnancy outcomes and/or obstetrical complications during and at the end of pregnancy.

Pregnancies that occur on study should be reported to The Antiretroviral Pregnancy Registry. More information is available at www.apregistry.com. [contact]; [contact]. Intrapartum complications and/or pregnancy outcome will be recorded to The Antiretroviral Pregnancy Registry as well as on study case report forms, if possible.

7.3 Unblinding

It is not expected that subject unblinding will be necessary for management of toxicity. If deemed medically appropriate, unblinding will be requested from the Data Center.

8.0 CRITERIA FOR DISCONTINUATION

8.1 Permanent Treatment Discontinuation

- Requirement for prohibited concomitant medications except vaccinations (see the Manual of Procedures).
- Requirement for precautionary concomitant medications at the discretion of the investigator (see the Manual of Procedures)
- Drug-related toxicity as per Section 7.1
- Study drug is discontinued for 7 consecutive days for reasons other than toxicity at the discretion of the investigator. If study drug is discontinued for reasons other than toxicity, but the underlying reason for the discontinuation later resolves, study drug may be resumed at the discretion of the investigator.
- Pregnancy or breast-feeding
- Request by subject to terminate treatment.
- Clinical reasons believed to be life threatening by the physician, even if not addressed in the toxicity Section of the protocol.

